### **Sample SAS Code for Tipping Point Analysis**

```
/*-----*/
```

```
/*--- Generate imputed data set for specified shift parameters ---*/
/*--- data= input data set ---*/
/*--- smin= min shift parameter ---*/
/*--- smax= max shift parameter ---*/
/*--- sinc= increment of the shift parameter ---*/
/*--- out= output imputed data set ---*/
/*-----*/
%macro midata( data=, smin=, smax=, sinc=, out=);
  data &out;
  set _null_;
run;

/*----- # of shift values -----*/
%let ncase= %sysevalf( (&smax-&smin)/&sinc, ceil );
/*----- Imputed data for each shift -----*/
%do jc=0 %to &ncase;
  %let sj= %sysevalf( &smin + &jc * &sinc);
  proc mi data=&data seed=xxx nimpute=m out=outmi;
    class trtp;
    monotone reg(y1 y2 y3);
    mnar adjust( y1 y2 y3 / shift=&sj adjustobs=(trtp='Placebo') ); *active treatment is
    used;
    var trtp y1 y2 y3;
  run;

  data outmi;
    set outmi;
    Shift= &sj;
  run;

  data &out;
    set &out outmi;
  run;
%end;
%mend midata;
```

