### 8.3.3.2.3. Tipping Point Analysis

Another sensitivity analysis – tipping point analysis will be considered to investigate the robustness of the result to departures from the missing at random (MAR) assumption of the MMRM model and to identify the tipping point where the treatment effect in participants with missing data overturns the treatment effect from statistically significant to statistically non-significant.

Hence the tipping point analysis will only be performed if the primary efficacy analysis is statistically significant in treatment effect.

Implementing the tipping point approach includes the following steps ([Yuan 2014, SAS Institute Inc.](#)):

- 1) Under the MNAR assumption, missing SDMT scores up to Day 84 will be imputed using PROC MI under MNAR.
- 2) The imputed values for observations in SAGE-718 treatment group will be adjusted directly using the shift parameter ( $\delta$ ).
- 3) The imputed datasets with the shift parameter applied will be analyzed using PROC MIXED.
- 4) The results will be combined for the inference using PROC MIANALYZE.
- 5) Step 1-4 will be repeated until the result is not statistically significant.
- 6) If needed, step 1-5 will be repeated with more stringent shift parameter applied until the result is not statistically significant.

The shift parameter ( $\delta$ ) value will start from 0 and decrease by 0.2 decrements until non-significant p-value is achieved. One hundred datasets will be generated.

The tipping point summary for each pairwise comparison will include LSmeans difference, the 95% CI, and p-value for each of  $\delta$  value. From  $\delta = (-3, 0)$ , iterations including the tipping point will be summarized.

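### The sample tipping-point code shifts the imputed placebo scores instead of the SAGE-718 scores, so with the planned deltas it can only help SAGE-718

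*SAP*

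**What the plan says.** SAP Section 8.3.3.2.3 states the aim: "tipping point analysis will be considered to investigate the robustness of the result to departures from the missing at random (MAR) assumption". It looks for the point at which missing-data assumptions change the result, in its words "overturns the treatment effect from statistically significant to statistically non-significant". Step 2 names the arm to be shifted: "The imputed values for observations in SAGE-718 treatment group will be adjusted directly using the shift parameter". The sign and step of delta are also fixed: it "value will start from 0 and decrease by 0.2 decrements until non-significant p-value is achieved". The range from -3 to 0 is to be summarized, using 100 imputed datasets. The analysis is conditional: "Hence the tipping point analysis will only be performed if the primary efficacy analysis is statistically significant in treatment effect".

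The SAP Appendix B macro for this analysis contains "mnar adjust( y1 y2 y3 / shift=&sj adjustobs=(trtp='Placebo". With the comment that follows, the same line reads "adjustobs=(trtp='Placebo') ); *active treatment is" and continues on the next line to say that this arm is the one used. The macro header, "macro midata( data=, smin=, smax=, sinc=, out", leaves the minimum, maximum and increment of the shift blank, so their values have to come from Section 8.3.3.2.3.

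SAP Section 8.3.1.1 scores the SDMT as a count of correct pairings, so a higher score is better.

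**The concern.** In PROC MI, `adjustobs` names the observations whose imputed values receive the shift. The option names placebo. The body text and the comment beside the option both name the active arm, and nothing else in the SAP supports shifting placebo.

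With delta at zero or below, the direction matters. Lowering imputed SAGE-718 scores penalises the drug, which is what a tipping-point analysis of a positive result has to do. Lowering imputed placebo scores rewards it. The analysis runs only after a significant primary result, so for a positive finding the code would start from significance and strengthen it at each step. A report that no tipping point was found could then be read as robustness, although no unfavourable departure from MAR had been tried.

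**Working it through.** **Inputs from SAP Section 5.2.** SD of change 7.3; design difference 4 points; two-sided alpha 0.05; 90% power; 71 evaluable and 89 randomized per arm; 20% dropout.

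**The plan's own figure.** n per arm = 2 × (1.960 + 1.282)² × 7.3² / 4² ≈ 70. At 71 per arm, power is 90.4% by the normal approximation and 90.0% by the noncentral t. 71 / 0.8 = 88.75, rounded up to 89 per arm or 178 in all. The sample size reproduces, and 7.3 is used below.

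**Direction.** Let D be the SAGE-718 minus placebo difference at delta = 0, and f the imputed fraction in the shifted arm.

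- SAGE-718 shifted (text): D + f × delta, which equals D - f|delta| when delta ≤ 0.
- Placebo shifted (code): D - f × delta, which equals D + f|delta| when delta ≤ 0.

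The two move in opposite directions whatever the value of f.

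**Assumptions for size, which the documents do not give.** D = 2.5, 3, 3.5 or 4. Equal imputed counts in both arms, above the 5% trigger in SAP Section 8.3.3.2: 5, 9 or 18 of 89 (5.6%, 10.1%, 20.2%), and 4, 7 or 14 of 71 (5.6%, 9.9%, 19.7%). The shift is applied directly at Day 84 only.

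**Formula.** With S = 2 × 7.3² / (n(1 - f)),

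z = (D ± f|delta|) / sqrt(S + f(1 - f) × delta² / n),

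plus for the code and minus for the text. The second variance term is the extra spread from moving only a fraction f of one arm. The threshold is 1.96.

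**Worked example: n = 89, 18 imputed, D = 2.5.**

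- S = 106.58 / 71 = 1.501, so z at delta = 0 is 2.5 / 1.225 = 2.04.
- At delta = -3, f|delta| = 0.607 and the variance is 1.501 + 0.016 = 1.517 (root 1.232).
- Code: 3.107 / 1.232 = 2.52. Text: 1.893 / 1.232 = 1.54.
- With SAGE-718 shifted, z is 1.97 at -0.4 and 1.94 at -0.6, so significance is lost at about -0.5.

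**Selected settings**

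| n per arm | Imputed per arm | D | z at 0 | z at -3, code | z at -3, text | Delta at which text version tips |
|---|---|---|---|---|---|---|
| 89 | 5 | 2.5 | 2.22 | 2.36 | 2.07 | -5.0 |
| 89 | 5 | 4 | 3.55 | 3.69 | 3.39 | -26.1 |
| 89 | 9 | 2.5 | 2.17 | 2.42 | 1.90 | -2.3 |
| 89 | 18 | 2.5 | 2.04 | 2.52 | 1.54 | -0.5 |
| 89 | 18 | 4 | 3.27 | 3.74 | 2.76 | -7.5 |
| 71 | 14 | 3 | 2.19 | 2.61 | 1.75 | -1.6 |
| 71 | 14 | 4 | 2.93 | 3.34 | 2.48 | -6.4 |

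**Full grid.**

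- Of 24 settings, 22 start significant. The other two are n = 71, D = 2.5 with 7 imputed (z = 1.94) or 14 imputed (z = 1.83).
- As coded, z is higher at -3 and at -10 than at 0 in all 22.
- For very large |delta| the coded z tends to sqrt(nf/(1 - f)), at least 2.06 on this grid. It never falls below 1.96 in any of the 22.
- With SAGE-718 shifted, all 22 tip, at deltas from about -0.5 to -26.1. Five tip by -3: n = 89 with D = 2.5 (9 or 18 imputed) and D = 3 (18 imputed); n = 71 with D = 2.5 (4 imputed) and D = 3 (14 imputed).

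**Simulation, direct Day 84 shift.** 600 datasets, true difference 4, 89 per arm, 18 imputed per arm, 100 imputations, Rubin's rules. At delta = 0, 546 were significant. At -3 the mean difference among those 546 moves by +0.607 as coded, with z higher in all 546 and none losing significance. It moves by -0.607 with SAGE-718 shifted, and 73 of 546 lose significance.

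**Simulation, shift carried through sequential imputation.** One dataset with a borderline result, 20% imputed per arm and an assumed within-participant correlation of 0.6: difference 2.27, p = 0.048 at delta = 0. At -3, p = 0.009 as coded (difference 3.02) and 0.187 with SAGE-718 shifted (difference 1.52).

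**The case against.** The best counter-argument concerns weight. The block is headed as sample code, the governing text is unambiguous, and the comment on the line agrees with the text, so this looks like a slip in one level name. The analysis is only to be considered, needs both a significant primary result and the missing-data trigger, and is left out of the forest plot (SAP Section 8.3.3.3). A programmer who follows the instruction to continue until significance is lost would probably notice that the p-value keeps falling. All of that stands and limits the severity. It does not remove the error: SAS executes the option and not the comment, this is the only code the SAP gives for the analysis, and a run stopped at -3 would simply show no tipping point.

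The size is also open to challenge:

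- In 17 of the 22 settings the corrected code stays significant at -3 as well, so the two versions often differ there in the p-value and not in the conclusion.
- The 0.17 to 0.61 point range is a Day 84 approximation. The macro shifts all three visits, and the sequential simulation gave about 0.75 where the simple formula gives about 0.60.
- Equal missingness is assumed. If placebo has few imputed values, the coded shift does almost nothing. Participants who stop treatment are asked to keep attending visits, so 20% imputed may be high.

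These points change the size of the movement. They do not change its direction.

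**Conclusion.** The concern holds. The `adjustobs` option contradicts SAP Section 8.3.3.2.3 and its own comment. Run with the planned deltas, the macro moves the result only toward SAGE-718 and cannot serve the stated purpose. The direction rests on the documents alone: the arm named in the option, the sign of delta and the scoring of the SDMT. Positive deltas on placebo would penalise SAGE-718, but the plan does not use them.

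The size rests on the assumed effects and imputed fractions and on the Day 84 approximation: 0.17 to 0.61 points the wrong way at delta = -3, a swing of twice that against the intended analysis. This should be fixed, but its reach is limited to one conditional sensitivity analysis. The primary analysis, alpha control and the other sensitivity analyses are not affected. The finding covers the `adjustobs` level and does not vouch for the rest of the macro.

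**What to change.** In the tipping-point macro in SAP Appendix B, set `adjustobs` to the SAGE-718 level of `trtp`, and run it with delta at zero or below as Section 8.3.3.2.3 specifies. Leave the text of that section as it is. Leave `modelobs=(trtp='Placebo')` in the control-based PMM-MI code unchanged, because there placebo is the intended reference arm.

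The cost is one option on one line, with no change to text, data or design. Making the correction before unblinding avoids any appearance that the result prompted it.

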## APPENDIX C. HANDLING OF MISSING DATES

Dates missing the day or both the day and month of the year will adhere to the following conventions in order to classify TEAEs and to classify prior and concomitant medications.

In general, listings will present the actual partial or missing values rather than the imputed values that may be used in derivation. In instances where imputed values will be presented, imputed values will be flagged.

### Adverse Events

If the AE start date is completely missing, do not impute a date but consider it as TEAE, unless the AE end date is before the initiation of treatment, in which case the AE will be considered prior.

For partial AE start dates:

- When the year is known, but the month and day is unknown, then:
  - If the year matches the year of first dose date and the end date (if present) is after first dose date, or AE is ongoing, then impute as the month and day of the first dose date.
  - If the year of AE onset < year of initiation of the treatment, then the month and day will be set to December 31st.
  - If the year of AE onset > the year of initiation of treatment, then the month and day will be set to January 1st.
- If the year and month are known, but the day is unknown, then:
  - If the year of AE onset = the year of initiation of the treatment and:
    - the month of AE onset = the month of initiation of the treatment, then the day will be set to the day of initiation of the treatment.
    - the month of AE onset < the month of initiation of the treatment, then the day will be set to the last day of month.
    - if the month of AE onset > the month of initiation of the treatment, then the day will be set to the 1st day of month.
  - If the year of AE onset < the year of initiation of the treatment, then the day will be set to the last day of month.
  - If the year of AE onset > the year of initiation of the treatment, then the day will be set to the 1st day of month.

If the imputed AE onset date is after the AE stop date, then the onset date will be set to the stop date.

- When the year and day are present and the month is missing, treat it as if the day is missing, and only year is present. Follow the imputation rules for “year is known, but the month and day is unknown”.
- When the year is missing, but the month and/or day is known, treat this date as missing; do not impute.

### Prior and Concomitant Medications

For the partial start date of medication:

- If the year is present and the month and day are missing, then the month and day will be set to January 1.
- If the year and day are present and the month is missing, then the month will be set to January.
- If the year and month are present and the day is missing, then the day will be set to the 1st day of month.
- If the imputed start date of medication is after the non-imputed end date of medication, then the start date will be set to the end date of medication.

For the partial end date of medication:

- If the year is present and the month and day are missing, then the month and day will be set to December 31.
- If the year and day are present and the month is missing, then the month will be set to December.
- If the year and month are present and the day is missing, then the day will be set to the last day of the month.
- If the year and day are present and the month is missing, then treat it as if the day is also missing. Set the month and day to be December 31.

## APPENDIX D. ANTIDOPAMINERGIC MEDICATIONS

A list of neuroleptics and anti-chorea medications which are commonly referred collectively as Antidopaminergic Medications (ADM) in the HD community.

### Anti-Psychotic Medications:

1. ARIPIPRAZOLE
2. CHLORPROMAZINE
3. FLUPHENAZINE
4. HALOPERIDOL
5. LUMATEPERONE TOSYLATE
6. OLANZAPINE
7. QUETIAPINE FUMARATE
8. QUETIAPINE
9. RISPERIDONE

### Anti-Chorea Medications:

1. DEUTETRABENAZINE
2. TETRABENAZINE
3. VALBENAZINE

## APPENDIX E. HI-DEF SCORING INSTRUCTIONS

The scoring algorithm of the Hi-DEF scales includes four steps: 1) rescore the item responses; 2) assigning scores for participants who do not work or drive due to HD; 3) calculation of the raw sum score; and 4) linking the raw scale scores to the Rasch-based interval level 0-100 score.

### Step 1: Rescoring the item responses

Before the scores can be calculated, the data from item responses should be rescored so as: (i) the lowest item-level score is zero, and (ii) the highest item-level score is four.

**Table 14. Item Rescoring | At home, At work, and Driving items**

	No difficulty	A little difficulty	Some difficulty	A lot of difficulty	Cannot do this anymore
Original scoring	1	2	3	4	5
Revised scoring	0	1	2	3	4

**Table 15. Item Rescoring | Communicating items**

	Never	Sometimes	Often	Almost always
Original scoring	1	2	3	4
Revised scoring	0	1	2	3

### Step 2: Assigning scores for participants who do not work or drive due to HD

If a participant indicates that they do not work or drive due to their HD, this implies the same principle as the highest response option on the Hi-DEF scale (i.e., they “Cannot do this anymore” due to their HD).

Participants who indicate that they i) do not work due to their HD or ii) do not drive due to their HD should therefore be rescored with the highest score (i.e., the score indicating the lowest level of functioning) for all items within the corresponding subscale (i.e., Driving or At work), as illustrated in the table below.

**Table 20 Assigned scoring – Participants who do not work or drive due to HD**

	Does not work due to HD	Does not drive due to HD
Original scoring	Missing on all Work scale items	Missing on all Driving scale items
Assigned scoring	Score of 4 (“Cannot do this anymore”) will be assigned for all Work items and Total score 44 for Total Work score	Score of 4 (“Cannot do this anymore”) will be assigned for all Driving items and Total score 32 for Total Driving score

### Step 3: Calculation of the raw score

The data to be used for the calculation of the Hi-DEF full scale scores are presented in the table below, with the number of items included in the scale, the minimum number of items needed for score calculation, and the range of the raw score (raw score is the simple sum of the item scores). The table also presents the corresponding item numbers as presented in the updated version of the scales.

**Table 21. Description of the Hi-DEF Scale Scores**

	Number of items	Number of items needed for score calculation	Raw score range	Corresponding item numbers from original 47-item version of the scale
Home	15	8	0–60	02, 03, 04, 05, 06, 07, 08, 09, 10, 11, 12, 13, 14, 15, 17
Work†	11	6	0–44	19, 21, 22, 23, 24, 25, 26, 27, 28, 29, 30
Driving‡	8	4	0–32	32, 33, 34, 35, 36, 37, 38, 39
Communicating	6	3	0–18	41, 42, 43, 44, 46, 47
Hi-DEF total score	40	21*	0–154	02, 03, 04, 05, 06, 07, 08, 09, 10, 11, 12, 13, 14, 15, 17, 19, 21, 22, 23, 24, 25, 26, 27, 28, 29, 30, 32, 33, 34, 35, 36, 37, 38, 39, 41, 42, 43, 44, 46, 47
Hi-DEF Short form	7	4	0–26	02, 04, 07, 09, 10, 41, 42

*\*Except for Work and Driving scales if the participant indicates they do not work or drive due to HD, in which case all items for the relevant scale (Work or Driving) are assigned a score of 4 ("Cannot do at all"), as explained in Step 2 above; †Assigned Work scale score = 44 for participants who indicated they do not work due to HD; ‡Assigned Driving scale score = 32 for participants who indicated they do not drive due to HD; ^As 21 items are needed to calculate the Hi-DEF total score, this score cannot be calculated if both Work and Driving scales are missing, unless both are missing as the participant does not work and drive due to HD, in which case the assigned scores explained in Step 2 are used to calculate the Hi-DEF total score*

## Hi-DEF subscales and short form

### Complete data

For complete data, for each participant, the responses for each subscale are added up (once rescored according to *Error!* Reference source not found. [Table 14](#) and [Table 15](#)) to produce a total raw score for each scale. Use the applicable conversion table, provided under Step 4.

### Missing data

If there is missing data as the participant does not work or drive due to HD, assign scores for the Work and Driving scales as explained in Step 2.

For data missing for other reasons, if there is more than 50% missing data, the data from the individual should be set to missing. If there is less than 50% missing data, the data can be imputed. For example, for the home scale (15 items),  $\geq 8$  items need to be completed and in the driving scale (8 items),  $\geq 4$  items need to be completed.

Use the following steps to produce a complete within-person response pattern (subscale total raw score):

1. Substitute the average raw score of the non-missing items for the missing item(s) value.
2. Calculate a sum total score for the domain and round to the nearest whole integer.

Following this you can move to Step 4 (score transformation).

## Hi-DEF Total score

To calculate a total score, the instructions above need to be followed for each subscale and then the 4 scores should be summed. Therefore, a total score can only be calculated for those participants who have completed at least half of the items in each of the four scales. If the participant does not work and does not drive for reasons other than due to their HD, a total score cannot be summed.

## Step 4: Score transformation

The conversion table transforms total raw scores to Rasch logit measure scores, which are subsequently mapped to a 0–100 scale for convenience. This conversion is a simple linear

transformation that changes the logit mean of the minimum to maximum scores and converts the most extreme measures to 0 and 100, respectively.

The applicable conversion tables below should be used to derive the corresponding measure score. The tables also show the crosswalk between the Hi-DEF short form and total score.

Raw score (complete data)	0-100 transformed score	Raw score (complete data)	0-100 transformed score
0	0	31	49
2	13	33	51
4	19	35	53
6	24	37	55
8	27	39	57
10	30	41	59
12	32	43	61
14	34	45	64
16	36	47	66
18	38	49	69
20	40	51	73
22	42	53	77
24	43	55	82
26	45	57	88

27	46
28	47
29	48
30	49

58	93
59	99
60	100

**Table 23 Work scale raw score to transformed score**

Raw score (complete data)	0-100 transformed
0	0
1	8
2	13
3	17
4	20
5	23
6	25
7	28
8	30
9	31
10	33
11	35
12	36
13	38
14	39
15	41
16	42
17	43
18	44
19	46
20	47
21	48
23	51
24	52
25	53
26	54
27	55
28	57
29	58
30	59
31	61
32	62
33	64
34	66
35	67
36	69
37	72
38	74
39	78
40	81
41	86
42	91
43	98
44	100

**Table 24 Driving scale raw score to transformed score**

Raw score (complete data)	0-100 transformed	Raw score (complete data)	0-100 transformed
0	0	17	49
1	10	18	50
2	17	19	52
3	22	20	53
4	27	21	55
5	30	22	56
6	33	23	59
7	35	24	62
8	37	25	65
9	39	26	70
10	40	27	75
11	42	28	80
12	43	29	84
13	44	30	89
14	45	31	94
15	47	32	100
16	48		

**Table 25 Communicating scale raw score to transformed score**

Raw score (complete data)	0-100 transformed
0	0
1	12
2	21
3	28
4	34
5	39
6	43
7	47
8	50
9	53
10	56
11	58
12	61
13	64
14	67
15	70
16	74
17	81
18	100

**Table 26 Crosswalk between Hi-DEF total score and short-form score raw score**

Total		Short form		Total		Short form		Total		Short form	
Raw score	0-100	Raw score	0-100	Raw score	0-100	Raw score	0-100	Raw score	0-100	Raw score	0-100
0	0			39	39			78	50		
1	7			40	40	8	40	79	51		
2	11	0	11	41	40			80	51		
3	14			42	40			81	51	15	51
4	16			43	41			82	51		
5	18			44	41			83	52		
6	19	1	19	45	41			84	52		
7	21			46	42	9	42	85	52		
8	22			47	42			86	52		
9	23			48	42			87	53		
10	24			49	43			88	53	16	53
11	25	2	25	50	43			89	53		
12	26			51	43	10	43	90	53		
13	27			52	43			91	54		
14	27			53	44			92	54		
15	28	3	28	54	44			93	54		
16	29			55	44			94	54	17	54
17	29			56	45			95	55		
18	30			57	45	11	45	96	55		
19	31			58	45			97	55		
20	31	4	31	59	45			98	55		
21	32			60	46			99	56		
22	32			61	46			100	56		
23	33			62	46			101	56	18	56
24	33			63	46	12	46	102	56		
25	34	5	34	64	47			103	57		
26	34			65	47			104	57		
27	35			66	47			105	57		
29	36			68	48			107	58	19	58
30	36	6	36	69	48	13	48	108	58		
31	36			70	48			109	58		
32	37			71	49			110	59		
33	37			72	49			111	59		
34	37			73	49			112	59		
35	38			74	49			113	60		
36	38	7	38	75	50	14	50	114	60		

37	39			76	50			115	60			154	100		
38	39			77	50			116	61						

